remain positive years after treatment has cleared microfilaremia. The antigen tests will be performed in individual residents over 5 years of age. This will be done by sampling approximately 100 randomly selected households per sentinel site (village) to produce N of 400. There will be 4 sentinel sites for each treatment zone (annual vs twice annual MDA). The target number of samples per village is close to the minimum sample size of 335 needed to show that the rate of antigenemia (card test) positivity is less than 2% (with 95% confidence and 80% power). In post-MDA populations, this corresponds to a MF rate of less than 0.5%, which is an LF elimination target. We expect to collect 4 to 5 blood samples per household. Subjects with positive card tests will be tested for microfilaremia with 60 µl night blood thick smears. Our decision to detect MF by thick smears of finger prick blood rather than membrane filtration of venous blood is because thick smears are recommended for LF elimination program guidelines. In addition, our prior studies in Egypt have shown that L3 production by *Culex* mosquitoes that feed on MF carriers with negative thick smears is negligible. The justification for collecting blood at night for MF testing is that microfilariae of *W. bancrofti* and *B. timori* in Indonesia are nocturnally periodic with highest counts in peripheral blood between 9 p.m. and 2 a.m.

Blood tests for *Brugia timori* infection *B. timori* infections will be detected by two methods, namely microscopic examination and the BrugiaRapid Test (BmR1 antibody) Cassette (Cellabs, Malaysia). Microscopic examination of thick blood smears prepared with 60 µl of blood collected between the hours of 9 p.m. and 2 a.m. The Brugia Rapid test is a rapid diagnostic test kit for detecting antibodies to filarial parasites using serum or whole blood.

Blood samples will be collected from randomly selected households per sentinel site (village) to produce N of 400. There will be 4 sentinel sites for each treatment zone (annual vs twice annual MDA). This sample size number exceeds the minimum target sample size of 335 needed to show that the MF rate is less than 2% (with 95% confidence and 80% power, assuming an actual rate of 0.5%, which is an LF elimination target). We expect to collect 4 to 5 samples per household.

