7.3 Participant Enrollment and Follow-Up

This project aims to enroll approximately 6,400 subjects per year for two study areas (total for *W. bancrofti* and *B. timori* sub-projects). Each of the two study areas (one for *Brugia and Wuchereria (Sikka)* and one for *Wuchereria (Java)*) will have cluster surveys of approximately 400 people per village for 4 villages from annual MDA areas and 400 people per village for 4 villages from twice per year MDA areas.

The community/household surveys are cross-sectional with no follow-up planned.

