With microfilaria (per 60 μ l of blood) measured as counts, we will display mean counts of microfilaria across the four sentinel sites from each treatment zone (annual vs. twice annual MDA) over years of observation including the baseline. To accommodate zero counts in modeling, we will use Geometric mean intensity (GMI) of circulating microfilaria. GMI is calculated as $\text{antilog}[(\sum \log(x+1))/n] - 1$, where x is the number of microfilaria per 60 mm^3 of blood and n is number of subjects. A generalized linear mixed model (GLMM) (implemented in PROC GLIMMIX) will be used to account for correlation of observations resulted from clustering. CONTRAST statements will be used to test the significance of differences in GMI of antigenemia between the two treatment regimens at each year of observation. The resulting estimates of GMI will be presented with 95% confidence interval. All statistical tests will be two-sided at a significance level of 0.05, but one-sided p-value will be reported according to the hypothesis. Similar analytic models will be done for community Mf loads and community egg load for each of three intestinal worm eggs.

The cost analysis comparing the two treatment regimens will be conducted by [name] of the George Washington University School of Public Health and Health Services. The model will also allow cost effectiveness analysis when combined with the efficacy analysis.

2. Testing secondary hypothesis

The secondary hypothesis is that twice annual MDA is superior to annual MDA in controlling STH. The primary endpoint for assessing the impact of MDA on STH infections is community egg load (average stool egg count per species). The analysis strategy for these end points is the same for microfilaria count in testing the primary hypothesis.

Adverse event

Since this is a minimal risk and nonintervention study, adverse events are not expected to be an issue. However, subjects will be monitored for adverse events related to blood collection. Proportion of subjects with an adverse event will be tabulated with 95% confidence interval for each sentinel site at each year of observation.

Treatment coverage rate

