Treatment coverage rate of the eligible population will be reported from the repeated cross-sectional surveys for the sentinel sites (villages) during different rounds of treatment. Differences in treatment coverage rates will be evaluated between the two treatment regimens (annual vs. twice annual MDA) over time with the use of Chi-square test.

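### The Chi-square test for treatment coverage names no adjustment for village or household clustering, so its type I error exceeds 5% by an amount that depends on an ICC the plan does not give

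*Combined protocol and SAP*

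**What the plan says.** The last paragraph of section 7.4, on treatment coverage, says that coverage of the eligible population "will be reported from the repeated cross-sectional surveys for the sentinel sites (villages) during different rounds of treatment". It continues: "Differences in treatment coverage rates will be evaluated between the two treatment regimens", with the comparison made "over time with the use of Chi-square test". It names no design effect, cluster-adjusted Chi-square, village-level test or mixed model.

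Section 7.3 describes the sample. Each study area "will have cluster surveys of approximately 400 people per village", with 4 villages under annual MDA and 4 under twice-yearly MDA. Section 4 says that regimen is set by treatment zone, with four sentinel villages in each, and expects 4 to 5 samples per household. Earlier in section 7.4: "All statistical tests will be two-sided at a significance level of 0.05".

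For the infection outcomes, the same section specifies a generalized linear mixed model because observations within a household and sentinel site are correlated. It extends similar models to community microfilaria and egg loads, but not to coverage.

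**The concern.** A Chi-square test on individuals counts each respondent as independent information. Here regimen does not vary between people within a village. Government health officials deliver MDA to communities, so people in one village or household can be expected to resemble each other in whether they were treated. Ordinary differences between villages then enter the regimen comparison, but the test's standard error makes no allowance for them. The mixed model for infection outcomes is a separate analysis, so it does not repair this one.

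The stake is interpretation. Section 2.2 links elimination to sustained coverage of at least 75% and suggests that accelerated programmes may improve compliance. A false coverage difference could seem to support that suggestion, or could be offered as the explanation for an efficacy difference.

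**Working it through.** **Inputs from the documents.** 400 people per village, 4 villages per regimen per area and two areas (section 7.3); two-sided alpha of 0.05 (section 7.4). A coverage of 75% is used for illustration only: section 2.2 gives it as a programme level, not as an expected study value.

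**Assumed.** The between-village ICC of coverage. The documents give none, and the sizing in section 7.2 is binomial. The range shown is 0.001 to 0.10.

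**Reproducing the plan's figure.** 2 areas × 2 regimens × 4 villages × 400 = 6,400 per year, which matches section 7.3. The plan states no sample size or power for the coverage test.

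**Formulas.**
- Design effect: DEFF = 1 + (400 − 1) × ICC.
- Actual two-sided type I error of the nominal 5% test: 2 × [1 − Φ(1.96/√DEFF)].
- Between-village SD at 75% coverage: √(ICC × 0.75 × 0.25).
- Effective number per regimen in one area: 1,600/DEFF.

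| Assumed ICC | Village SD (points) | DEFF | Effective n | Actual type I error |
|---|---|---|---|---|
| 0.001 | 1.4 | 1.40 | 1,144 | 9.8% |
| 0.002 | 1.9 | 1.80 | 890 | 14.4% |
| 0.005 | 3.1 | 3.00 | 534 | 25.7% |
| 0.01 | 4.3 | 4.99 | 321 | 38.0% |
| 0.02 | 6.1 | 8.98 | 178 | 51.3% |
| 0.05 | 9.7 | 20.95 | 76 | 66.8% |
| 0.10 | 13.7 | 40.90 | 39 | 75.9% |

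A beta-binomial simulation (40,000 runs per setting; coverage 60%, 75% and 85%; 4 or 8 villages per regimen) agrees within 1 point. Pooling both areas does not help, because the inflation depends on the number per village and not on the number of villages.

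**Where the error passes 50%.** This needs 1.96/√DEFF = 0.6745, so DEFF = 8.44 and ICC = (8.44 − 1)/399 = 0.0187. At 75% coverage that is a village SD of about 5.9 points.

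**Household clustering alone.** With 4 people per household and assumed household ICCs of 0.2, 0.4 and 0.6, DEFF = 1 + 3 × ICC = 1.6, 2.2 and 2.8. The type I error is 12%, 19% and 24%.

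**The village-level alternative.** A t-test on village percentages held its simulated type I error between 4.6% and 5.2% for every ICC tried from 0 to 0.10. For precision at 75% coverage:
- The unadjusted Chi-square calls a difference of 1.96 × √(0.1875 × 2/1,600) = 3.0 points significant (2.1 points with both areas pooled).
- The 4 v 4 t-test has a 95% half-width of 2.447 × √[2 × (SD² + 0.1875/400)/4]. This is about 9, 11 and 18 points for village SDs of 5, 6 and 10 points.
- The interval widens by √DEFF × 2.447/1.96: 1.73 × 1.25 = 2.2 times at ICC 0.005, and 4.58 × 1.25 = 5.7 times at ICC 0.05.

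**The case against.** **The test may be only under-described.** The plan does not say that the test is unadjusted or how the data enter it, and a Rao-Scott statistic is also a Chi-square test. The individual-level reading is an inference. It is the natural one, though: no adjustment is named, and the same section spells out its clustering method where it wants one.

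**The villages may be the whole target.** If inference stops at these particular sentinel villages, differences between them are real rather than chance, and the relevant clustering is within households. That lowers the inflation but does not remove it: 12% to 24% under the assumed household ICCs.

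**A reader might infer that the test will usually declare chance village differences to be regimen differences.** The documents do not support that. It needs an ICC of about 0.019 or more. A village SD of about 6 points is not extreme, but nothing in the plan establishes it, and at an ICC of 0.01 or less the rate for a single test is below half.

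**Coverage is secondary.** It belongs to neither hypothesis, and no decision rule or efficacy model uses this p-value. That stands and limits the severity. Any effect on how efficacy is read is a risk of interpretation, not a planned use.

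**The village-level test is not a full remedy.** That also stands. Regimen is set by zone, so anything shared by all four villages in a zone stays in the comparison.

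**Conclusion.** The concern holds as a defect of the stated test: wrong as written, for a supporting process measure. The direction is certain if there is any positive correlation within villages or households. The size is conditional: the type I error is about 2 to 15 times nominal over assumed village ICCs of 0.001 to 0.10. These rates are for one test. Repeating it over rounds and areas raises the chance of at least one false finding, by an amount that depends on how persistent village effects are. The point does not bear on the validity of the infection-outcome analyses, and it should be corrected before coverage is compared.

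**What to change.** Replace the Chi-square sentence in section 7.4 with one of two analyses:
- a t-test on village coverage percentages within each area, 4 v 4 villages with 6 df; or
- a logistic mixed model with random village and household effects, regimen-by-time terms and small-sample degrees of freedom.

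State in advance which rounds or which yearly coverage measure are compared. The twice-yearly arm has two rounds a year while the surveys are annual, so a comparison by round is not defined across arms. Report coverage by village, and the regimen difference with its 95% CI. Add a sentence saying that regimen is set by treatment zone, so the analysis does not remove an effect shared by all villages in a zone.

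The cost is a few sentences and no new data. The downside is precision: with the 6-df t-test, intervals are about 2.2 to 5.7 times wider than the unadjusted ones over ICCs of 0.005 to 0.05, and modest coverage differences will often not be distinguishable from village variation.

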8 SUBJECT CONFIDENTIALITY

Subject confidentiality will be strictly held in trust by the participating investigators and staff. This confidentiality is extended to cover testing of biological samples in addition to the clinical information relating to participating subjects. This project does not include genetic testing. The study protocol, documentation, data and all other information generated will be held in strict confidence. No information concerning the study or the data will be released to any third party without prior written approval of the DOLF Principal Investigator.

Study monitors or sponsor representatives may inspect all documents and records required to be maintained by the investigator at any time during or after the completion of the study.

Data privacy control:

- 1- Every individual will have one unique bar code identifier.
- 2- Every sample collected in the field will be labeled with barcode stickers linked to ID number.
- 3- The Laboratory will test and report results using sample numbers, not names or ID.
- 4- Person names and identifying information will be directly entered into Smart phone, and the information will be synchronized daily from these devices to a laptop with a flash drive backup. Names will be removed automatically from the standard project database and will be kept in a separate database that will be password protected and accessed only by the Indonesian Project Data Manager (PDM) to be identified in response to a written request from the DOLF PI ([name]), the Objective 1 PI ([name]) or country PI ([name]). This is not expected to be a common event and will only be necessary if there are questions about discrepancies between serial/sample numbers and ID numbers.
- 5- The Data Management Team will be responsible for ensuring that no one in the project can link the the unique bar code identifier with the enrolled person except the PDM and others listed in #4 above. Person ID's will not be released for use in other projects.
- 6- The data server will keep a log file/data audit trail that will indicate the time/date and identify for every access to the data files. No one outside the Data Management Group will be able to modify any data on the server, and unauthorized persons will not be able to access any of the data files.

- 7- Each computer, Smartphone with project data will have a separate password. Also, each database will have an access system with user names and passwords that will control the level of access and permissions for each user. The PDM is responsible for controlling these permissions, and she/he is the only one that can change this.

8.1 Future Use of Stored Specimens

Residual specimens (serum, blood smears) will be maintained after the study is completed. Samples will be stripped of unique identifiers and stored in endemic country laboratories or in the PI's laboratory at Washington University. . Sequencing will be performed with DNA isolated from a small number of stool or blood samples to detect and characterize worm parasite DNA (blood or stool) and bacterial DNA (stool). The samples will be deidentified prior to any sequencing procedures. In addition, all human DNA sequences will be filtered out prior to bioinformatic analysis and no genetic testing of humans will be performed.

9 INFORMED CONSENT PROCESS

We will follow procedures outlined in the **DHHS Regulation on Informed Consent 45 CFR Part 46 - Subpart A, 46.116** (<http://www.hhs.gov/ohrp/humansubjects/guidance/45cfr46.htm#46.116>).

Informed consent (IC) is a process that is initiated prior to the individual's agreeing to participate in the study and continuing throughout the individual's study participation. Study physicians will read the consent script (with potential risks and benefits) in a locally understood language to subjects and their families and leave a copy of this with each family. The consent document will be reviewed and approved by project IRB's prior to initiation of the study. Study physicians will discuss risks and possible benefits of participation in this study with subjects and their families. Study physicians will explain the purpose of the study to subjects and answer any questions that may arise. The subjects may withdraw consent at any time during the course of the study. The rights and welfare of the subjects will be protected by emphasizing to them that the quality of their medical care will not be adversely affected if they decline to participate in this study.

9.1 Informed Consent/Assent Process (in Case of a Minor or Others Unable to Consent for Themselves.

Inclusion of minor children in community surveys will require consent from at least one parent plus assent of the child.

Human studies for this project are pending at FWA registered IRBs at Washington University ([name]) and at IRB of the Faculty of Medicine of the University of Indonesia ([name]); no human studies will be conducted prior to approval by both IRBs.

Filarial antigen tests: Binax Now Filariasis Card Test and/or Alere Filariasis Strip Test using finger prick blood (75-100 μ L) will be performed in the laboratory according to the kit protocol and read at 10 minutes.

Antifilarial Antibody Testing: The Brugia Rapid Test detects antibodies to filarial parasite with finger prick blood (25 μ L for serum/ 35 μ L for whole blood). This test will be performed in field sites or in a laboratory according to the kit protocol and read at 15 minutes for serum and 20 minutes for whole blood.

Stool samples for STH examination: Stool samples will be collected in 25 ml containers and preserved in formalin (final concentration 5%). One gram of stool will be examined using the FLOTAC method [10]. This method provides a sensitive means of detecting and quantifying helminth eggs.

Specimen archive: In addition to new samples generated during this study, the Laboratory will be responsible for maintenance of archived samples (used Binax Now Filariasis Card Test, preserved stool samples, etc.) collected during the DOLF project.

QC activities: DOLF investigators will visit study sites to review procedures and results. They will also keep in close contact with Indonesian counterparts by email, telephone, and during visits by collaborating scientists from Indonesia to the USA. All samples will be tested in the endemic country laboratories. Some preserved stool samples and questionable blood smears will be tested in parallel in the reference laboratory at Washington University.

Standard Operating Procedures Summary (SOP) for Data Collection and Field Work

Field work will be conducted by trained physicians and paramedical personnel who will be trained for data and blood collection.

All field team members will be trained by staff physicians with assistance from other project personnel:

1. All field epidemiology personnel (physicians, technicians and field workers) will be trained in GCP topics for research involving human subjects.
2. Field and laboratory personnel will also be trained regarding proper procedures for collecting blood, for preparing blood smears, for performing filarial antigen tests, and for labeling specimens (barcode stickers).
3. Field data will be entered in the field using electronic questionnaires on PDAs or smart telephones. Finger-prick blood (400 µl) will be collected by physicians or trained technicians for laboratory studies. All samples will be labeled in the field.
